6.3 Appendix 3: Changes to Protocol-Planned Analyses

Not applicable.

6.4 Appendix 4: Demographic and Baseline Characteristics

Demographic and baseline characteristics will be summarized by intervention group in Study AMAX and by the intervention in the originating study for the mITT/PAS population; no testing will be performed for baseline characteristics. Summaries are to include values from the baseline of the originating studies and, for values that are expected to change over time, Visit 1 of AMAX. The summary of additional participant characteristics and subgroup analysis will not require an amendment to the SAP. For continuous measures, summary statistics will include sample size, mean, standard deviation, median, minimum, and maximum. For categorical measures, summary statistics will include sample size, frequency, and percentages.

			Baseline Sum	mary
Variable	Continuous Summary	Categorical Summary	Originating Studies	Study AMAX
Demographic Chara	cteristics			
Age ^a	Yes	<65 years, ≥65 years	X	X
		<40 years, ≥40 years	X	X
Sex	No	Male, Female	X	
Age within Sex	No	Male <40 years, Male ≥40 years	X	X
		Female <40 years, Female ≥40 years		
Ethnicity	No	Hispanic/Latino, Non- Hispanic/Non-Latino	X	
Race	No	American Indian/Alaska Native, Asian, Black/African American, Native Hawaiian or other Pacific Islander, White, or Multiple	X	
Geographic	No	North America, Europe, Other	X	X
Region ^b		By Country (listed in other documents)	X	X
		Asia, North America, Central America/South America, Europe and ROW (rest of world)	X	X

			Baseline Sum	mary
Variable	Continuous Summary	Categorical Summary	Originating Studies	Study AMAX
Height (cm)	Yes	None	X	
Weight (kg)	Yes	<80 kg, ≥80 kg	X	X
		<100 kg, ≥100 kg	X	X
BMI ^c	Yes	Underweight (<18.5 kg/m2), Normal (≥18.5 and <25 kg/m2), Overweight (≥25 and <30 kg/m2), Obese (≥30 and <40 kg/m2), Extreme obese (≥40 kg/m2)	X	X
Tobacco use	No	Never, Current, Former	X	X
Prior CD Therapy				
Prior biologic exposure	No	Ever, Never	X	
Prior biologic failure ^d	No	Failed, not failed	X	
Inadequate response or loss of response to a biologic	No	Ever, Never	X	
Inadequate response to a biologic	No	Ever, Never	X	
Loss of response to a biologic	No	Ever, Never	X	
Number of prior biologics used	Yes	0, 1, 2, >2	X	
Number of failed ^d biologics	Yes	0, 1, 2, >2	X	
Prior biologic failure ^d and prior biologic exposure	No	Not exposed, Exposed but not failed, Exposed and failed at least one	X	

			Baseline Sum	mary
Variable	Continuous Summary	Categorical Summary	Originating Studies	Study AMAX
Baseline CD Therapi	es			
Baseline corticosteroid use	No	Yes, No	X	X
Baseline prednisone equivalent dose	Yes	None	X	X
Budesonide	No	Yes, No	X	X
Baseline use of methotrexate	No	Yes, No	X	X
Baseline Disease Cha	aracteristics			
Duration of CD ^e	Yes	<1 year, ≥1 to <5 years, ≥5 years	X	X
Age at Diagnosis of CD ^f	Yes	<10 year, ≥10 to <17 years, ≥17 years to <40 years, ≥40 years	X	
Baseline Disease Location	No	Ileal, Colonic, Ileal-colonic	X	
Baseline Fecal Calprotectin	Yes	≤250 μg, >250 μg/g	X	X
Baseline C-reactive Protein (CRP)	Yes	≤10 mg/L, >10 mg/L	X	X
Baseline SES-CD	Yes	SES-CD (<12, ≥12)	X	X
Baseline AP average	Yes	AP average ($\langle 2, \geq 2 \rangle$	X	X
Baseline SF average	Yes	SF average (<7, ≥7)	X	X
Baseline CDAI average	Yes	CDAI total score (<300, ≥300)	X	X
Baseline IBDQ Total Score and Domain Scores	Yes	None	X	X

			Baseline Sum	mary
Variable	Continuous Summary	Categorical Summary	Originating Studies	Study AMAX
CC				

Abbreviations: AP = abdominal pain; BMI = body mass index; CD = Crohn's disease; CDAI = Crohn's Disease Activity Index; eCRF = electronic case report form; IBDQ = Inflammatory Bowel Disease Questionnaire; PCS = physical component summary; SF = stool frequency.

- ^a Age in years will be calculated as length of the time interval from the imputed date of birth (July 1st in the year of birth collected in the eCRF) to the informed consent date.
- b Ethnicity will only be reported for participants within the United States.
- ^c Body Mass Index (BMI) will be calculated as: $BMI(kg/m^2) = Weight(kg)/(Height(m))^2$.
- d Failure defined as reasons for prior treatment discontinuation are: loss of response, inadequate response or intolerance to medication.
- e Length of the interval from the date of CD diagnosis to the date of informed consent.
- f Age at diagnosis in years will be calculated as the time interval from the imputed date of birth (July 1 in the year of birth collected in the eCRF) to the date of CD diagnosis.

6.5 Appendix 5: Study Intervention Compliance

Study intervention compliance for each participant will be calculated as:

$$Treatment\ compliance\ (\%) = 100\ \times \frac{Total\ number\ of\ infusions\ administered}{Total\ number\ of\ infusions\ planned\ per\ protocol}$$

Here the planned drug administrations per protocol is based on the number of visits before the participant discontinued study drug. Each participant will be defined as having received a dose on a given date if they received at least 80% of the planned dose as derived from the Exposure eCRF page.

Study intervention compliance with investigational product will be summarized for the mITT/PAS population. Deviations from the prescribed dosage regimen will be described in a listing.

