6.1. Study Intervention(s) Administered

The doses and routes of administration reflect the multipart study design (Section 4.1).

This table lists the intervention used in this clinical study

Intervention Name	Mirikizumab
Dosage Level(s)	CCI
Route of Administration	IV infusion or SC injection
Authorized as defined by EU Clinical Trial Regulation	Authorized in EU and not used according to the marketing authorization

Packaging and Labeling

Study interventions will be supplied by the sponsor in accordance with current Good Manufacturing Practice. Study interventions will be labeled as appropriate for country requirements.

All investigational products will be stored, inventoried, reconciled, and destroyed according to applicable regulations. Clinical trial materials are manufactured in accordance with current Good Manufacturing Practices.

- Single-use solution vial containing mirikizumab with study-specific labels.
 - The CCI vial of mirikizumab is manufactured to deliver CCI
- Single-use solution prefilled syringe containing mirikizumab.
 - The CCI syringe of mirikizumab is manufactured to deliver CCI
 - The CCI syringe of mirikizumab is manufactured to deliver CCI

Vials and syringes will be supplied in cartons, with the appropriate quantity specific to the planned dispensing schedule. Investigational product will be provided with study-specific labels.

Preparation and Administration

Sites must have resuscitation equipment, emergency medications, and appropriately trained staff available during the infusion and monitoring period. All participants should be monitored for 1 hour or longer after IV dosing, according to investigator practice or local standard of care.

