This is an open-label extension study with no randomization. Participants from Study AMAM are assigned to either mirikizumab SC or mirikizumab IV followed by SC based on their endoscopy response status at Week 52 in Study AMAM. Participants from Study AMAG are assigned to mirikizumab SC. Therefore, no intervention comparisons or formal hypothesis testing will be done. Analyses and summaries will be focused on point estimates and confidence intervals.

3 Sample Size Determination

The sample size of Study AMAX will be determined by the number of participants who enroll in Study AMAX from the preceding studies (Study AMAM and Study AMAG). It is anticipated that approximately 50% to 70% of the eligible participants will be enrolled from Study AMAM and Study AMAG. Based on this assumption, 640 to 900 participants are expected to enter Study AMAX.

4 Analysis Sets

For purposes of analysis, the analysis sets are defined in the table below.

Population	Description	
Modified Intent-to-	Definition: All enrolled participants who take at least 1 dose of study	
Treat (mITT)	intervention, even if the participant does not receive the correct study	
Population ¹	intervention, or otherwise does not follow the protocol. Participants	
	will be analyzed according to the assigned treatment arms described in	
	Section 5.1.4.	
	Purpose: Used for sensitivity analyses of efficacy, health outcomes	
	and quality of life measures.	
Primary Analysis	Definition: All patients from the mITT population who	
Set (PAS)		
Population ¹	Purpose: Used for primary analyses of efficacy, health outcomes and	
	quality of life measures.	
Safety Population ¹	Definition: Same as mITT Population.	
	Purpose: Safety analysis will be conducted on this population.	
Sub-Populations ^{1,2}	Definition: All participants in the PAS (or mITT or Safety) population	
of PAS (or mITT or	who meet the criteria for the endpoints being examined (an example,	
Safety)	the study primary endpoint, the endoscopic response at Week 52 in	
	AMAX, a subset population will be the endoscopic responders at Week	
	52 of the originating study). Participants will be analyzed according to	
	the assigned treatment arms described in Section 5.1.4.	
	Purpose: Used for efficacy, health outcomes, quality of life measures	
	and may be used for safety analysis.	

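### The compliance formula counts infusions only, so it is undefined for participants on SC dosing alone and covers just three doses in re-induced participants

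*SAP*

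**What the plan says.** SAP Section 6.5 opens with "Study intervention compliance for each participant will be calculated as" and then prints a percentage: infusions administered in the numerator, infusions planned in the denominator. Three statements follow it:

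- On the denominator: "Here the planned drug administrations per protocol is based on the number of visits before the participant discontinued study drug".
- On what counts as a dose: a participant has "received a dose on a given date if they received at least 80% of the planned dose", taken from the Exposure eCRF page.
- On reporting: "Study intervention compliance with investigational product will be summarized for the mITT/PAS population". Dosing deviations go into a separate listing.

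Protocol Section 9.4.2.4 promises the deviation listing and leaves the remaining compliance details to the SAP.

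On routes, the table in Protocol Section 6.1 gives "IV infusion or SC injection". SAP Section 2 (Statistical Hypotheses) says "Participants from Study AMAM are assigned to either mirikizumab SC or mirikizumab IV followed by SC", according to endoscopic status at AMAM Week 52, and "Participants from Study AMAG are assigned to mirikizumab SC". SAP Section 5.7.3 gives the re-induction course as three IV doses.

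**The concern.** The formula is meant for every participant, but its unit is the infusion, and a large part of the study population has no infusion planned in AMAX. For those participants the ratio has a zero denominator. For re-induced participants it stops at the IV course and says nothing about the SC dosing that fills the rest of up to three years.

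The planned compliance summary is what is at stake. A programmer who follows the text cannot fill the SC-only columns. In the re-induced columns, a participant who received all three infusions scores 100% whatever happened afterwards. Much of the later dosing is self-administered at home, which is where a reader of a long-term extension would most want to see compliance.

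**Working it through.** The documents state no compliance figure, so there is none to reproduce. The check is to apply the printed ratio to each regimen.

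**Inputs**

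- Formula: 100 × infusions administered / infusions planned (SAP 6.5).
- Regimens: SC only, or IV followed by SC (SAP Section 2); three IV doses (SAP 5.7.3).
- Groups: SAP 5.1.4 lists eight non-pooled AMAM sequences, namely miri/miri, PBO/miri, uste/uste and PBO/PBO, each with an SC and an IV version. Four are SC only and four are IV followed by SC. The miri/miri/SC group carries the co-primary label.
- Office visits: 19, from Week 0 to Week 156 (SAP Appendix 9).
- Dosing interval: every 4 weeks. This is an assumption for the SC phase, because the dose weeks are redacted.

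**Step 1: SC-only participants.** Infusions planned = 0 and infusions administered = 0, so compliance = 100 × 0/0, which is undefined. This applies to 4 of 8 AMAM sequences and to all AMAG participants. It needs no assumption about the interval.

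**Step 2: is the 4-week assumption consistent with the documents?** Weeks 0 to 156 in steps of 4 give 156/4 + 1 = 40 dose times. Subtracting 19 office visits leaves 21 between-visit doses. Table AMAX.10-1 (Protocol Appendix 12) has 21 between-visit rows with a 7-day tolerance and no visit number: 5 (after V4 to V8) + 3 (after V9 to V11) + 12 (two after each of V12 to V17) + 1 (after V18). The two counts agree. Protocol Section 8.2.7.1 also describes the at-home dosing as monthly.

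**Step 3: re-induced participants.** IV at Weeks 0, 4 and 8, then SC from Week 12. The ranges depend on whether the endpoint visit itself carries a dose.

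| Horizon | Planned doses | Doses in the formula | Share covered |
|---|---|---|---|
| Week 52 | 13 (3 IV + 10 SC) or 14 (3 IV + 11 SC) | 3 | 3/13 = 23.1% or 3/14 = 21.4% |
| Week 156 | 39 or 40 | 3 | 3/39 = 7.7% or 3/40 = 7.5% |

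**Step 4: illustration.** A re-induced participant receives all three infusions and then misses some SC doses by Week 52. The numbers missed are assumptions.

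| SC doses missed | Printed formula | All planned doses |
|---|---|---|
| 1 | 3/3 = 100% | 12/13 = 92.3% or 13/14 = 92.9% |
| 2 | 3/3 = 100% | 11/13 = 84.6% or 12/14 = 85.7% |
| 3 | 3/3 = 100% | 10/13 = 76.9% or 11/14 = 78.6% |

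**The case against.** The best reply is that the word infusions is left over from another setting. The sentences after the formula are neutral as to route: they speak of drug administrations, of a dose on a date, and of investigational product. Read as a whole, the appendix points to all doses, and on that reading nothing is numerically wrong. That is probably what was intended. But the ratio prints the wrong unit twice, and neither document shows another compliance percentage that could replace it. Protocol Section 10.13.7 describes how compliance is assessed in continued access (questioning, syringe counts, log review) but gives no percentage. A separate table specification may exist, but it was not available here.

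It is also fair to say that naming the co-primary group could suggest a threat to the co-primary result. There is none. The group is named only because its compliance column would be empty.

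Two further remarks bear on the correction. First, a denominator of all scheduled doses marks down a participant whose doses were withheld under the protocol's own rules. The present text does not exclude such doses either, so this does not rescue the formula, but the corrected wording should settle it. Second, continued access has its own dosing table and should be stated to be in or out of scope.

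Basing planned administrations on visits before discontinuation is not a second error. It reads most naturally as a cut-off, and the protocol names between-visit doses by visit interval. It would still help to say that home doses are counted.

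**Conclusion.** The concern holds as a minor error in a planned descriptive analysis. As printed, the formula gives no value for any SC-only participant and covers only the three IV doses for re-induced participants. Neither statement needs an assumption. The percentages (21–23% of doses covered by Week 52, 7.5–7.7% by Week 156) rest on the assumed 4-week interval, which the between-visit row count and the description of home dosing support. If infusions is read as administrations over all scheduled doses, the numerical problem disappears.

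The consequence is confined to the compliance summary. No estimand, analysis-set definition visible in the documents, or efficacy estimate uses the percentage, and dosing deviations are still listed.

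**What to change.** Replace the ratio in SAP Section 6.5 with:

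Compliance (%) = 100 × (IV and SC doses received, under the existing 80%-per-date rule) / (all IV and SC doses scheduled in the Schedule of Activities and Table AMAX.1-4, at the office and at home, up to study drug discontinuation or data cutoff).

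In the same edit, state whether doses withheld under the protocol count as planned, and whether the continued access period is included.

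The cost is a line or two of SAP wording and minor programming. No new data are needed: home doses are recorded on the administration log and transcribed to the eCRF (Protocol Section 6.1.1), and the 80% rule already uses the Exposure page. The change should be made before the compliance tables are programmed.

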6.6 Appendix 6: Clinical Trial Registry Analyses

Additional analyses will be performed for the purpose of fulfilling the Clinical Trial Registry (CTR) requirements.

Analyses provided for the CTR requirements include the following:

Summary of adverse events (AEs), provided as a dataset which will be converted to an XML file. Both serious adverse events (SAEs) and 'Other' AEs are summarized by study intervention group, by MedDRA PT.

- An AE is considered 'Serious' whether or not it is a TEAE.
- An AE is considered in the 'Other' category if it is both a TEAE and is not serious. For each SAE and 'Other' AE, for each term and study intervention group, the following are provided:
 - o the number of participants at risk of an event
 - o the number of participants who experienced each event term
 - o the number of events experienced.
- Consistent with www.ClinicalTrials.gov requirements, 'Other' AEs that occur in fewer than 5% of participants/subjects in every study intervention group may not be included if a 5% threshold is chosen (5% is the minimum threshold).
- Adverse event reporting is consistent with other document disclosures (e.g., the CSR, manuscripts, and so forth.

6.7 Appendix 7: CDAI Questionnaire

The CDAI score is calculated for each week using the algorithm below (Best et al. 1976). The standard weights can be determined using the Standard Weight table on the following page.

FOR REVIEW PURPOSES ONLY

Questionnaire obtained by:	Study ID	Subject Number	Visit/Cycle Number	Signature of Individual Completing Form
Lilly	Investigator Number	Page 1 of 1		Date Signed by Individual Completing Form

Patient reported outcomes in Crohn's disease

			DAY				7 Day Total	Weighting Factor	Total
1	2	3	4	- 5	6	7		93	
								x 2 =	
					.0			x 5 =	
	ž		3		5			x 7 =	
t								Check all th	at appl
									0
pyodema	a gangreno	osum,aphth	ous stoma	titis					il i
r abscess	S								
									Q.
OF) durin	g past 7 da	ays							
						Total n	umber of ch	ecked boxes=	2
								x 20 =	
in the las	t 7 days						No	= 0, Yes = 1	
								x 30 =	05 24
					None	= 0, Quest	tionable = 2	, Definite = 5	
0.00								x 10 =	A A
ole)								gative, enter 0	
								x 6 =	8
				Per	centage de	eviation fro	m standard	weight x 1 =	
	pyoderm: pr abscess	pyoderma gangren or abscess 20F) during past 7 d	pyoderma gangrenosum,aphthor abscess 20F) during past 7 days	nt pyoderma gangrenosum,aphthous stomator abscess DOF) during past 7 days	1 2 3 4 5 Int Int Int Int Int Int Int In	1 2 3 4 5 6 pyoderma gangrenosum,aphthous stomatitis or abscess OF) during past 7 days I in the last 7 days None	1 2 3 4 5 6 7 pyoderma gangrenosum,aphthous stomatitis or abscess OF) during past 7 days Total number of the last 7 days None = 0, Questole)	Total To	Total Factor 1 2 3 4 5 6 7

© 2014 John Wiley & Sons Ltd

[figure not shown]
Standard Weight Table Based on Height and Sex

WOM				
Height in cm without shoes	Standard Weight in Kg			
148	53.1			
149	53.6			
150	54.1			
151	54.5			
152	55.0			
153	55.4			
154	55.9			
155	56.4			
156	57.0			
157	57.5			
158	58.1			
159	58.6			
160	59.1			
161	59.6			
162	60.2			
163	60.7			
164	61.3			
165	61.9			
166	62.4			
167	62.9			
168	63.4			
169	63.9			
170	64.5			
171	65.0			
172	65.5			
173	66.0			
174	66.6			
175	67.2			
176	67.7			
177	68.3			
178	68.8			
179	69.3			
180	69.8			
181	70.3			
182	70.9			
183	71.5			
184	72.1			
185	72.7			
186	73.4			

ME	
Height in cm without shoes	Standard Weight in Kg
158	62.6
159	62.9
160	63.3
161	63.7
162	64.1
163	64.6
164	65.0
165	65.5
166	66.0
167	66.6
168	67.1
169	67.6
170	68.1
171	68.7
172	69.2
173	69.7
174	70.3
175	70.8
176	71.3
177	71.9
178	72.4
179	73.0
180	73.6
181	74.3
182	74.8
183	75.5
184	76.2
185	76.9
186	77.6
187	78.2
188	78.8
189	79.6
190	80.4
191	81.0
192	81.6
193	82.2
194	82.8
195	83.4
196	84.0

Modified for height without shoes from the 1983 Metropolitan Life Insurance Ideal Weights for Height tables.

6.9 Appendix 9: Study Visit or Week Definition for Daily Diary

CDAI-SF, CDAI-AP, CDAI Well-Being, CCl and additional measures are collected using Patient Daily Diary, entries will be mapped to study week by the following:

Visit Number /	Diary Data	Start Day	End Day
Week Number	Collection		
Baseline ¹		NA	NA
Visit 1 ¹ / Week 0		NA	NA
Visit 2 / Week 4	Electronic Diary	Max (Date of First Dosing, Week 4	Week 4 Assessment
		Assessment Date – 28 days	Date – 1 day
Visit 3 / Week 8	Electronic Diary	Max (Week 4 Assessment Date, Week	Week 8 Assessment
		8 Assessment Date – 28 days	Date – 1 day
Visit 4 / Week 12	Electronic Diary	Max (Week 8 Assessment Date, Week	Week 12 Assessment
		12 Assessment Date – 28 days	Date – 1 day
Visit 5 / Week 20 ²	1-Day paper diary	NA	NA
Visit 6 / Week 28 ²	1-Day paper diary	NA	NA
Visit 7 / Week 36 ²	1-Day paper diary	NA	NA
Visit 8 / Week 44 ²	1-Day paper diary	NA	NA
Visit 9 / Week 52	14-Day paper	Max (Week 44 Assessment Date, Week	Week 52 Assessment
	diary	52 Assessment Date – 28 days	Date – 1 day
Visit 10 / Week 60 ²	1-Day paper diary	NA	NA
Visit 11 / Week 68 ²	1-Day paper diary	NA	NA
Visit 12 / Week 76	14-Day paper	Max (Week 68 Assessment Date, Week	Week 76 Assessment
	diary	76 Assessment Date – 28 days	Date – 1 day
Visit 13 / Week 88 ²	1-Day paper diary	NA	NA
Visit 14 / Week 100	14-Day paper	Max (Week 88 Assessment Date, Week	Week 100 Assessment
	diary	100 Assessment Date – 28 days	Date – 1 day
Visit 15 / Week 112 ²	1-Day paper diary	NA	NA
Visit 16 / Week 124	14-Day paper	Max (Week 112 Assessment Date,	Week 124 Assessment
	diary	Week 124 Assessment Date – 28 days	Date – 1 day
Visit 17 / Week 136 ²	1-Day paper diary	NA	NA
Visit 18 / Week 148 ²	1-Day paper diary	NA	NA
Visit 19 / Week 156	14-Day paper	Max (Week 148 Assessment Date,	Week 156 Assessment
	diary	Week 156 Assessment Date – 28 days	Date – 1 day

¹ Baseline will be the Baseline from AMAM or AMAG. For Visit 1 the summarized value for each relevant variable will be the last available value for the patient from study AMAG or AMAM.

